Experimental Design (Figure 1). A 12-week randomized, placebo-controlled, double-blind design study with lanthanum (starting dose of 1,500-3,000 mg/day according to baseline serum phosphorus; up-titrated monthly as needed based on serum phosphorus) will be conducted. After providing informed consent, subjects will undergo screening prior to study start. Subjects who meet inclusion criteria will have baseline measurements performed as described below. Measurements will be made under supine, overnight fasted (water only) conditions. Patients will then be randomly assigned to receive either lanthanum or placebo (see dosing below). Allocation to the active drug versus placebo group will be random, and a stratification process will be used on the basis of baseline FMD_{BA} of <4% and $\geq 4\%$ to protect against a baseline imbalance that would not

be well handled by other statistical procedures. With counseling and adherence monitoring from a nurse, subjects will maintain their baseline diet throughout the study, including intake of phosphate of <1,000 mg/day. Measurements will then be repeated after 12 weeks. The investigators involved in the acquisition and analysis of key outcomes will be blinded to the treatment assignment of the subjects as well as serum phosphorus levels.

Figure 1:

Subjects will come to the lab at the UPI Building on 9 separate occasions:

- **Session 1:** Screening measurements, complete 3 day diet record
- **Session 2:** Baseline measurements
 - Resting arterial blood pressure and blood sampling of circulating markers (see below)
 - Venous endothelial cell collection (for subsequent protein measurements)
 - FMD_{BA} (endothelium-dependent dilation) and aortic PWV (arterial stiffness), with and without acute inhibition of oxidative stress via systemic i.v. infusion of ascorbic acid [vitamin C])
 - Endothelium-independent dilation (EID) to sublingual nitroglycerin
 - Begin study treatment (lanthanum or placebo)
- **Sessions 3-8:** Weekly/monthly check-in (see below)
- **Session 9:** Identical to Session 2 (note: subjects will not take a dose the a.m. prior to testing session)
 - **Subjects will also complete a second 3 day diet record**

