a) Oxidative Stress-Associated Suppression of EDD and Large Elastic Artery Stiffness: The influence of oxidative stress on FMD_{BA} and aPWV will be determined by infusing a supraphysiological dose of ascorbic acid (vitamin C; American Regent Laboratories Inc.) or isovolumic saline, as described previously by the PI's doctoral training laboratory and others^{63, 72-74}. A priming bolus of 0.06 g ascorbic acid/kg fat-free mass (FFM) dissolved in 100 mL of saline will be infused intravenously at 5 mL/min for 20 minutes, followed immediately by a "drip-infusion" of 0.02 g/kg FFM dissolved in 30 mL of saline administered over 60 minutes at 0.5 mL/min. Vascular measurements will be made at the end of the 20 min bolus during the "drip infusion" when peak plasma concentrations of ascorbic acid occur (34). The difference in FMD_{BA} and aPWV during ascorbic acid vs. saline infusion will be taken as a measure of the modulation of EDD/stiffness by oxidative stress^{63, 72}.

Risks of this procedure include: Ascorbic acid has been infused intravenously without any unfavorable side effects into young and older healthy subjects, as well as patients with chronic cardiovascular diseases. However, administration of concentrated ascorbic acid may cause irritation to the local area around the infusion. In order to reduce this risk we will dilute the infusion of ascorbic acid in sterile saline.

Justification: Infusing ascorbic acid is a safe, effective and established method of acutely inhibiting oxidative stress. As the difference in our primary outcome measures (FMD_{BA} and aPWV) in the presence of ascorbic acid vs. saline is an index of a modulation of EDD/stiffness by oxidative stress, we will be provided with mechanistic insight into the physiological adaptations contributing to any improvements in vascular function with phosphorus lowering. Specifically, less of an improvement in EDD/stiffness with ascorbic acid post- vs. pre-treatment, in the presence of improved EDD/stiffness during saline infusion post- vs. pre-treatment, would indicate that reduced oxidative stress contributed to the improvements in vascular function with phosphorus lowering.

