Analysis Populations: The primary analysis will be intention-to-treat. The data will also be analyzed as per protocol. Subjects randomized to treatment who receive at least one drug dose and complete baseline measurements will be included in the intention-to-treat analysis, regardless of whether they adhered to the assigned intervention. In the per protocol analysis, only those subjects who were adherent to the protocol (completed all 12 weeks of drug or placebo) and completed the end of the study measurements will be included. Decisions to remove subjects from the per protocol analysis set will be made prior to breaking the treatment blind. The intention-to-treat analysis will analyze subjects as randomized; the per protocol analysis will analyze subjects as treated.

Prior to all analyses, data checks will be conducted to verify or correct assumptions about the data structure and to identify potential issues with the data being collected. This process will include range checks

to identify impossible values (e.g., age=0) and cross-tabulations identifying relations between key variables. Differences between groups at baseline will be assessed by unpaired t-tests and changes in response to lanthanum vs. placebo by ANOVA for repeated measures. In the case of a significant F-value, post hoc tests will be performed using the Newman-Keuls method. The influence of changes in 2° outcomes (blood pressure, mechanistic variables, etc.) on changes in 1° outcomes in response to lanthanum will be examined by multiple linear regression. Potential confounders, such as changes in other characteristics that are known to influence vascular function (e.g. body mass, blood pressure) will be handled using ANCOVA. Alpha for the two primary endpoints will be set at 0.025 while there will be no adjustment for secondary outcomes as they will be considered exploratory.

G. Summarize Knowledge to be gained:

The findings from the proposed research should provide important new information regarding the potential benefits of phosphorus lowering upon the reduction of vascular dysfunction in patients with CKD. It should also provide important insight into the mechanisms involved in the modulation of EDD by elevated phosphorus. Together, this information will add to the knowledge of how to prevent and treat vascular dysfunction in patients with CKD.

H. References:

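### As the plan reads, the mechanistic regression puts the change in the saline reading on both sides, which favours Hypothesis 2 even when there is no drug effect and no mechanism

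*Combined protocol and SAP*

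**What the plan says.** All references are to the main protocol (13-0328).

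- **Section I, Hypothesis 2** is an association: vascular improvement in the lanthanum group goes with lower oxidative stress.
- **IV.D, Secondary (Exploratory) Outcomes, item a)** defines the infusion measure: "The difference in FMD_{BA} and aPWV during ascorbic acid vs. saline infusion will be taken as a measure of the modulation of EDD/stiffness". Its justification treats the two readings as versions of the primary measures: "As the difference in our primary outcome measures (FMD_{BA} and aPWV) in the presence of ascorbic acid vs. saline".
- The same justification gives the rule of interpretation. The first part is "less of an improvement in EDD/stiffness with ascorbic acid post- vs. pre-treatment". The second is that this, "in the presence of improved EDD/stiffness during saline infusion post- vs. pre-treatment, would indicate that reduced oxidative stress contributed to the improvements".
- **IV.C, Experimental Design** lists for Session 2, and by reference Session 9, "FMD_{BA} (endothelium-dependent dilation) and aortic PWV (arterial stiffness), with and without acute inhibition of oxidative stress". It describes no replicate saline reading and no separate non-infusion reading.
- **IV.F** regresses changes in the primary outcomes on changes in secondary ones: "The influence of changes in 2° outcomes (blood pressure, mechanistic variables, etc.) on changes in 1° outcomes in response to lanthanum". It mentions no shared component. Secondary outcomes are tested at two-sided 0.05, unadjusted, as exploratory.
- **IV.A, Outcome Measures** also plans a between-group comparison of the pre/post differences in FMD and aPWV under normal and inhibited oxidative stress.

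**The concern.** Write S for the saline reading, A for the ascorbic-acid reading and R = A - S for the response. If the primary outcome is S and R is a predictor, the regression relates dS to dA - dS, where d is the 12-week change. A chance rise in S raises the outcome and lowers the predictor by the same amount. The resulting negative association is the one Hypothesis 2 predicts for FMD; for aPWV, where improvement is a fall, the mirror image holds. The test of zero slope therefore has the wrong null value.

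The rule in IV.D shares the weakness in milder form, because a better S and a smaller R are not separate observations. At stake is the infusion part of Aim 2: a chance-positive primary result would tend to bring some mechanistic support with it.

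**Working it through.** The plan gives no figure for this association, so there is none to reproduce.

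**Inputs from the documents.** R = A - S (IV.D, item a); one reading with and one without ascorbic acid per session (IV.C); 20 completers per group (IV.C, Power); two-sided alpha 0.025 for each primary outcome and 0.05 for secondary outcomes (IV.F).

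**Assumed.** rho = correlation of dS and dA within a patient, taken from 0 to 0.9; equal variances s² unless stated.

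**Regression with no drug effect and no mechanism.**

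- cov(dS, dR) = rho·s² - s² = -(1 - rho)s²
- var(dR) = 2s²(1 - rho)
- correlation = -(1 - rho)/sqrt(2(1 - rho)) = -sqrt((1 - rho)/2)
- slope of dS on dR = -(1 - rho)/(2(1 - rho)) = -0.5

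Simulated rejection rates for a one-predictor regression at two-sided 0.05 (20,000 null data sets per setting; n = 20 is the lanthanum completers, n = 40 both arms):

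| rho | expected r | n = 20 | n = 40 |
|---|---|---|---|
| 0 | -0.71 | 96% | >99% |
| 0.5 | -0.50 | 64% | 93% |
| 0.8 | -0.32 | 28% | 52% |
| 0.9 | -0.22 | 15.5% | 28% |

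*Unequal variances.* With k = SD(dA)/SD(dS), r = (rho·k - 1)/sqrt(1 + k² - 2·rho·k). At rho 0, k = 0.5 gives -0.89 and k = 2 gives -0.45. The sign stays negative while rho·k < 1; at rho 0.8 the bias vanishes at k = 1/0.8 = 1.25 and reverses above that.

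*Check of cause.* When the response is computed from a second saline reading with independent error, rejection at n = 20 returns to 4.8% to 5.2%. The shared reading is the cause.

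**The IV.D rule at arm level, 20 per arm, no effect.** The between-arm effects on S and R have the same correlation, -sqrt((1 - rho)/2). Both point the predicted way with probability 1/4 + arcsin(sqrt((1 - rho)/2))/(2π). A significant saline improvement has probability 0.025/2 = 0.0125. Conditional rates are rounded from simulation and the bivariate normal, which agree within about two percentage points.

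| rho | both directions as predicted | R falls significantly, given S significantly better | both significant |
|---|---|---|---|
| 0 | 37.5% | about 42% | 0.0125 × 0.42 = 0.5% |
| 0.5 | 33% | about 22% | 0.0125 × 0.22 = 0.3% |
| 0.8 | 30% | about 11% | 0.0125 × 0.11 = 0.1% |
| 0.9 | 29% | about 8% | 0.0125 × 0.08 = 0.1% |

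Without conditioning, R falls significantly in 2.5% of null trials, so the between-arm test of R taken alone keeps its level.

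**The case against.** **The regression target is inferred.** IV.F does not name the ascorbic-acid response, and the oxidative-stress markers also fit its wording. No passage says outright that the primary value is the saline reading; the FMD description in IV.D mentions no infusion. A separate non-infusion primary reading would remove the shared error. This stands as a limit. But the response is item a) of the secondary outcomes and is offered there as mechanistic insight, and IV.C lists no other reading, so the inference is the natural one.

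**A valid infusion analysis is already planned.** This stands. The between-group comparison in IV.A is randomised and sound taken alone. A reader might infer that the whole infusion part of Aim 2 is invalid; the documents do not support that.

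**The IV.D rule is seldom met by chance.** This stands too. A reader might infer that the rule would usually confirm Hypothesis 2 with no effect. It would not: the signs agree in 29% to 37.5% of null trials and both are significant in about 0.1% to 0.5%. The inflation arises given a chance-positive saline result. If a true effect of 1.2 SD shifts both readings equally, the conditional rate is only 2.6% to 3.0% (rho 0 to 0.8).

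**The size is uncertain.** rho and the variance ratio are not given, and IV.F specifies multiple regression without saying whether it is confined to lanthanum patients. A reader might infer that a false association is near certain; that holds only near rho 0.

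**The outcomes are exploratory.** That label explains the lack of multiplicity adjustment. It does not repair a test whose null slope is not zero, and Section I makes mechanism the key secondary goal.

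**Conclusion.** The concern holds for the IV.F regression as the plan most naturally reads. Under equal variances, the nominal 5% test rejects in about 15.5% to 96% of null trials with 20 completers, in the direction of Hypothesis 2. This rests on three things: the response being among the predictors, the primary value being the same saline reading, and an assumed rho of 0 to 0.9. A sufficiently more variable ascorbic-acid change would weaken or reverse the bias.

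For the IV.D rule the fault is milder. It is not usually met under the null, but after a chance-significant saline improvement the response also falls significantly in about 8% to 42% of trials rather than 2.5%, so it is not independent support.

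The primary tests and the circulating and endothelial-cell markers are untouched. The change is worth making because it removes a bias toward the hypothesis at almost no cost.

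**What to change.** - **IV.F:** exclude the ascorbic-acid response as a predictor of change in saline FMD or aPWV. Use in that regression the independently measured oxidative-stress markers already collected: endothelial-cell nitrotyrosine, p47phox and the SOD isoforms (IV.D, item b) and the circulating markers of oxidative damage such as F2-isoprostanes (IV.D, item c).
- **Infusion experiment:** keep the randomised between-arm comparison of IV.A as the analysis, and report the arm effects under saline and under ascorbic acid with confidence intervals.
- **IV.D, item a):** state that a smaller response alongside an improved saline reading shares the saline measurement and is not independent evidence of mechanism.

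Agreement of the markers need not be made a condition: a null marker result does not by itself refute a functional infusion finding.

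The cost is wording in two sections and no new data. The downside is that the mechanistic claim becomes harder to make.

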Cardiovascular disease (CVD) is significantly increased in chronic kidney disease (CKD) and is an important cause of morbidity and mortality.¹⁻⁵ As much as 80% of all CVD is associated with vascular dysfunction,⁶ particularly impaired endothelium-dependent dilation (EDD),⁷ measured by brachial artery flow-mediated dilated (FMD_{BA}).^{8,9} Not surprisingly, patients with CKD demonstrate these dysfunctional vascular phenotypes. In CKD, phosphorus remains within the normal range (2.5-4.5 mg/dL) until late in the disease.¹⁰⁻¹³ In earlier stages of CKD, serum phosphorus levels are maintained with the normal range by up-regulating fibroblast growth factor 23 (FGF23) and a consequent increase in the fractional excretion of phosphorus by the kidney.¹⁰⁻¹³ However, elevated serum phosphorus, even within the normal range, is associated with adverse CVD outcomes in CKD.¹³⁻¹⁵ Elevations in serum phosphorus have also been associated with impaired EDD and with indirect measures of arterial stiffness.¹⁶⁻¹⁹ Whether lowering serum phosphorus with phosphate binders in patients with CKD will change phosphorus balance and improve EDD and arterial stiffness is unknown.

This investigation is an extension of a 12-week prospective, randomized, placebo-controlled double-blind trial (Phosphorus Lowering RCT, COMIRB 13-0328) that assesses the effects of phosphorus lowering with the phosphate binder, lanthanum carbonate, in stage IIIb and IV CKD with normal or modestly elevated serum phosphorus (2.8-5.5 mg/dL) on vascular endothelial function and arterial stiffness. The primary goal of the current Phosphorus Balance protocol is to determine whether lowering serum phosphorus (accomplished during the parent Phosphorus Lowering RCT) with a low phosphorus diet and 12 weeks of treatment with lanthanum carbonate, a non-absorbed, non-calcium-containing phosphate binder, affects phosphorus balance. The key secondary goal is to determine if differences in phosphorus balance affect vascular function as measured by FMD_{BA}.

To ensure adequate enrollment, we will also recruit patients with stage IIIb and IV CKD with normal or modestly elevated serum phosphorus (2.8-5.5 mg/dL) who are *not* currently participating in the parent Phosphorus Lowering RCT (COMIRB 13-0328). Similar to the Phosphorus Lowering RCT, these patients will follow a low phosphorus diet and will be randomized to lanthanum carbonate or placebo for 12 weeks (run-in period) prior to beginning the current Phosphorus Balance protocol.

Hypothesis A. Subjects with stages IIIb and IV CKD and normal or modestly elevated serum phosphorus (2.8-5.5 mg/dL) who are treated with 12 weeks of lanthanum carbonate and a low phosphorus diet will be in negative phosphorus balance compared to subjects treated with placebo.

Hypothesis B.

Improvements in EDD will correlate with negative phosphorus balance.

Aim A. To determine phosphorus balance in subjects with stage IIIb or IV CKD after being treated with lanthanum carbonate and a low phosphorus diet or placebo and a low phosphorus diet for 12 weeks.

Aim B. To determine whether phosphorus balance in each treatment group correlates with the FMD_{BA} measurement performed at the end of the proposed Phosphorus Balance protocol.

II. Background and Significance:

Risk of cardiovascular diseases (CVD) is significantly elevated in patients with chronic kidney disease (CKD); however, the increased cardiovascular risk in this patient population is only partially explained by traditional cardiovascular risk factors.¹⁻⁶ In earlier stages of CKD, serum phosphorus levels are maintained within the normal range by up-regulating fibroblast growth factor 23 and a consequent increase in the fractional excretion of phosphorus by the kidney.¹⁰⁻¹³ However, elevated serum phosphorus even within the normal range, as is the typical case in CKD patients not requiring chronic hemodialysis, has emerged within the last decade as a novel, independent predictor of CVD risk and associated mortality.¹³⁻¹⁵ Furthermore, little is known about phosphorus balance and its association with outcomes in CKD.

CKD patients also exhibit vascular endothelial dysfunction and increased arterial stiffness,^{20,21} two independent predictors of future CVD. A modest elevation in serum phosphorus contributes to this phenotype of vascular dysfunction.¹⁶⁻¹⁹ Recent evidence supports that an acute increase in serum phosphorus impairs endothelium dependent dilation (EDD) and increases vascular oxidative stress.¹⁶ In addition, both vascular endothelial dysfunction and increased oxidative stress have been identified as important predictors of mortality and cardiovascular events in patients with CKD.^{22,23} Thus, reducing serum phosphorus burden in CKD patients not requiring chronic hemodialysis may reduce cardiovascular events by improving vascular endothelial function and reducing large elastic artery stiffness. However, it is currently unknown if reducing serum phosphorus to a low normal laboratory range (<2.8 mg/dL) with oral phosphate binders induces negative phosphorus balance thus, potentially enhancing vascular function in this population.

Little is known about phosphorus balance in CKD. It is assumed that CKD patients remain in neutral phosphorus balance despite decreases in kidney function. Serum phosphorus increases but remains within the normal range¹⁰⁻¹³ until late in CKD thus making it difficult to recognize perturbations of phosphorus balance in these patients. Indeed, elevated serum phosphorus even within the normal range is associated with worse CVD outcomes.^{12,14,15} In CKD subjects with normal serum phosphorus treated with six weeks of sevelamer, a non-calcium based phosphate binder, serum phosphorus did not change significantly (3.45 ± 0.65 mg/dL vs. 3.31 ± 0.64 mg/dL) but there was a significant decrease in total urinary phosphorus excretion (534 ± 137 mg/24 hours vs. 313 ± 135 mg/24 hours, $p < 0.05$) as well as in parathyroid hormone (PTH) (107 [79-130] pg/mL vs. 69 [47-94] pg/mL, $p < 0.05$) and fibroblast growth factor 23 (FGF23) (103 [62-142] pg/mL vs. 54 [38-94] pg/mL, $p < 0.05$), suggesting a shift in phosphorus homeostasis.²⁴ However, two recent calcium balance studies performed in subjects with CKD stages III-IV, showed that subjects remained in neutral phosphorus balance despite administration of calcium-

containing phosphate binders.^{25,26} There are no studies evaluating the effect of non-calcium based phosphate binders on phosphorus balance in subjects with CKD nor other studies examining the effects of changing phosphorus balance on vascular function. Whether longer-term (12 weeks) treatment with non-calcium based phosphate binders induces a negative phosphorus balance in subjects with CKD is uncertain. It is also unknown if negative phosphorus balance improves vascular function.

III. Preliminary Studies/Progress Report:

Serum phosphorus is related to cardiovascular disease events and mortality as well as measures of arterial stiffness

Presented below is the longitudinal relationship between higher serum phosphorus and all-cause mortality and CVD events (myocardial infarction, stroke and peripheral vascular disease), and a cross-sectional association of elevated serum phosphorus with worsening pulse pressure (PP). These data were obtained from the Homocysteine Study in Advanced Kidney Disease (HOST), which was a prospective, randomized, double-blind study on the effects of folate, vitamin B₆, and vitamin B₁₂ replacement on all-cause mortality and CVD events in VA patients with severe CKD and elevated homocysteine.²⁷ As the intervention did not have an effect on the proposed outcomes, it represented a unique opportunity to convert the data obtained from a randomized control trial into an observational study. The HOST dataset has detailed information on demographics, CVD risk factors, prevalent CVD, circulating markers (including serum calcium, phosphorus, and intact parathyroid hormone), and usage of cardioprotective medications in all study participants. In addition, an endpoints committee adjudicated all endpoints. For the purpose of this analysis, we included 1,099 HOST participants. The mean (\pm SD) age of the participants was 69 \pm 11 years, 98% were male, and 26% were black. The mean estimated MDRD-GFR was 18 \pm 6 mL/min/1.73 m² and most participants (n=718; 65%) had an estimated MDRD-GFR of 15-29 mL/min/1.73 m². The mean serum phosphorus concentration was 4.3 \pm 1.3 mg/dL; 36% and 12% had a serum phosphorus concentration greater than 4.5 and 5.5 mg/dL, respectively. **These descriptive data demonstrate that poor vascular function and CVD events are associated with high serum phosphorus.**

Higher serum phosphorus levels are independently associated with CVD events/mortality in patients with advanced CKD: During a median follow-up of 2.9 years, 472 (42.9%) patients died from any cause and 237 (21.6%) had a CVD event. Higher serum phosphorus levels were positively associated with higher risks for the composite of death and CVD events. Identical results were observed when CVD events were examined separately (not shown). Compared to the lowest quartile, the two highest quartiles of serum phosphorus were associated with a significantly elevated risk for the composite endpoints, after multivariate adjustment (Table 1; hazards ratios (HR)). The analysis was repeated using serum phosphorus levels as a continuous variable instead of quartiles. After multivariable adjustment (Model 3), the HR of the composite endpoint increased by 1.17 (95% CI; 1.02-1.33; p=0.02) per 1 mg/dL increase in serum phosphorus. These results provide important support to my aim to evaluate whether changes in phosphorus lowering affect vascular endothelial function and arterial stiffness (two independent predictors of CVD events/mortality) in patients with advanced CKD.

Table 1. Association of Higher Serum Phosphorus with Risk of Cardiovascular Events & Death in the HOST Study

| Phosphorus Concentrations | Q1 | Q2 | Q3 | Q4 |
|---------------------------|----|----|----|----|
|---------------------------|----|----|----|----|

| | (≤3.5 mg/dL) | (3.6-4.1 mg/dL) | (4.2-4.8 mg/dL) | (>4.9 mg/dL) |
|----------------|--------------|-------------------|-------------------|------------------|
| Model 1 | 1.00 | 1.35(0.87- 2.09) | 1.70 (1.12- 2.57) | 1.93(1.29- 2.90) |
| Model 2 | 1.00 | 1.36 (0.88- 2.11) | 1.79(1.18-2.73) | 2.18(1.44-3.31) |
| Model 3 | 1.00 | 1.19 (0.76-1.86) | 1.50 (1.01-2.31) | 1.68 (1.05-2.68) |

Model 1: Unadjusted; **Model 2:** Adjusted for age, gender and race; **Model 3:** Adjusted for covariates in Model 2 plus smoking, diabetes, hypertension, prevalent CVD, body mass index, systolic and diastolic blood pressure, treatment arm, eGFR, albumin, calcium, 25-hydroxyvitamin D, intact PTH, LDL-cholesterol, high density lipoprotein-cholesterol, triglycerides and use of angiotensin converting enzyme inhibitors, angiotensin receptor blockers and β -blockers.

In addition, we performed a cross-sectional analysis of the relationship between serum phosphorus and pulse pressure (PP) in the HOST cohort. The results confirm that higher serum phosphorus levels are independently associated with a wider PP in patients with advanced CKD. The mean (\pm SD) PP in this population was 71 (20) mmHg. In adjusted linear regression models (Model 3), each 1 mg/dL increase in serum phosphorus was associated with a 2 mmHg increase in PP ($\beta=2.0\pm6.9$; $p=0.005$). These data support the notion that serum phosphorus lowering should reduce large elastic artery stiffness, as increased PP is an expression of arterial stiffness.

[figure not shown]
Feasibility of lanthanum carbonate treatment to lead to a sufficient separation in mean serum phosphorus between groups

[name], Clinical Assistant Professor in the Division of Renal Diseases and Hypertension at the University of Colorado Denver, recently examined the effects of phosphate binders on parameters of mineral metabolism among patients with moderate to advanced CKD. A total of 148 patients (eGFR 20-45 ml/min/1.73m²) were randomly assigned to calcium acetate (n=30), lanthanum carbonate (n=30), sevelamer (n=30), or placebo (n=58). The primary endpoint was change in mean serum phosphorus from baseline to the average measured at months 3, 6, and 9. Serum phosphorus decreased from a baseline mean of 4.2 mg/dL (for both active and placebo arms) to 3.9 mg/dL in the active therapy arm and 4.1 mg/dL in the placebo arm ($p=0.03$). These results were published in a peer-reviewed journal.²⁸ Differences in serum phosphorus between the placebo and the lanthanum carbonate arms were further analyzed at 3 months. Serum phosphorus decreased from a baseline of 4.2 mg/dL (for both the lanthanum carbonate and placebo arms) to 3.7 mg/dL in the lanthanum carbonate arm and to 4.1 mg/dL in the placebo arm ($p=0.04$). The mean dose of lanthanum carbonate was 2.7 g/day. An increase in serum phosphorus of 0.3-0.5 mg/dL has been associated with a significant increase in relative risk of all-cause mortality and CVD events in various epidemiologic studies of patients with CKD. These data suggest that the treatment with lanthanum carbonate will lead to a sufficient and significant separation in the mean serum phosphorus between groups.

There is a significant difference in FMD_{BA} and aPWV between healthy individuals and those with CKD

FMD_{BA} is a well-established intermediate endpoint and validated means with which to examine CVD in subjects with and without CKD. In Figure 1 we demonstrate that among 8 men studied by our group with stage III-IV CKD (aged 63 \pm 4 years) compared to 8 healthy age-matched control subjects (aged 60 \pm 3 years), there was a significant difference in FMD_{BA} (* $p<0.05$). These preliminary data are additional experimental evidence supporting the testing of therapeutic interventions that improve FMD_{BA} in patients with stage III-IV CKD.

Figure 1

IV. Research Methods

A. Outcome Measure(s): The proposed investigation is an extension of a 12-week prospective, randomized, placebo-controlled double-blind trial (Phosphorus Lowering RCT) of 60 subjects that assesses the effects of the phosphate binder, lanthanum carbonate, and a low phosphorus diet in stage IIIb and IV CKD with normal or modestly elevated serum phosphorus (2.8-5.5 mg/dL) on vascular endothelial function and arterial stiffness. Vascular endothelial function is assessed as endothelium-dependent dilation via FMD_{BA}. Subjects with stage IIIb and IV CKD with normal or modestly elevated serum phosphorus (2.8-5.5 mg/dL) who are *not* participating in the Phosphorus Lowering RCT will also be enrolled and will be treated with either lanthanum carbonate or placebo and a low phosphorus diet for a 12-week run-in period prior to initiating the current Phosphorus Balance protocol in order to mimic the parent Phosphorus Lowering RCT. After completion of 12 weeks of either lanthanum carbonate and a low phosphorus diet or placebo and a low phosphorus diet, 24 research subjects (12 treated with lanthanum carbonate and 12 treated with placebo) will participate in the proposed Phosphorus Balance Study. The primary outcome is the difference in phosphorus balance between the active and placebo groups. Serum phosphorus is not expected to change during the current Phosphorus Balance protocol as subjects will remain on the same dose of active drug or placebo that they were on during either the parent Phosphorus Lowering RCT or the 12-week lanthanum carbonate or placebo run-in period. The dose of active drug or placebo was titrated during the first month of the parent Phosphorus Lowering RCT or the 12-week run-in period and is expected to be stable during months 2 and 3 of both the parent RCT and 12-week run-in period as well as during the current Phosphorus Balance protocol. Secondary outcomes include whether there is a difference in FMD_{BA} between the active and placebo groups and whether this correlates with a difference in phosphorus balance between the active and placebo groups.

B. Description of Population to be Enrolled:

Subjects. A group of 24 subjects who have completed the 12-week parent Phosphorus Lowering RCT or the 12-week run-in period described above will provide written informed consent and serve as subjects for the current Phosphorus Balance protocol. Major inclusion/exclusion criteria are presented below:

Inclusion Criteria:

1. Completed prospective, randomized, placebo-controlled double-blind trial, Phosphorus Lowering to Treat Vascular Dysfunction in Chronic Kidney Disease (COMIRB #13-0328) or willing to participate in 12-week run-in period
2. Aged 40-79 years; women must be post-menopausal (serum phosphorus increases after menopause in women⁵⁸)
3. CKD stage IIIb or IV (eGFR by 4-variable MDRD prediction equation: 15-45 mL/min/1.73m²); stable renal function in the past 3 months
4. Mini-mental state examination (MMSE) score ≥24 (cognitive function screening); ability to provide informed consent

Exclusion Criteria:

1. Subjects with advanced CKD requiring chronic dialysis
2. Subjects at high risk for gastrointestinal events or alteration in gastrointestinal anatomy (e.g., history of gastrointestinal surgery, colon cancer), hypomotility disorders (e.g., constipation, ileus), current bowel obstruction, or fecal impaction
3. Significant co-morbid conditions that lead the investigator to conclude that life expectancy is less than 1 year
4. Expected to undergo living-related kidney transplant in the next 6 months
5. History of severe congestive heart failure (i.e., EF < 35%)
6. History of severe liver disease (i.e., elevated bilirubin, AST, ALT, or evidence of liver cirrhosis on biopsy or imaging)
7. Hospitalization in the past 3 months
8. BMI ≥40 kg/m² (FMD measurement can be inaccurate in severely obese subjects)
9. Active vitamin D analogue use (i.e., calcitriol, paricalcitol, doxercalciferol)
10. Alcohol dependence or abuse (i.e., as documented in subject's chart per PCP or mental health provider or if stipulated by subject)
11. Current tobacco abuse (i.e., current and habitual use of any tobacco product)
12. Use of prednisone and other immune suppressant medications (i.e., current and ongoing use of prednisone or other immune suppressant medication)

A Standard Operating Procedure is in place that prohibits the use of nitroglycerin (NTG) in subjects with systolic blood pressure <100 mmHg and with migraine headache. Additionally, it is part of the Standard Operating Procedure that subjects are educated regarding drugs that interact with lanthanum carbonate (levothyroxine, quinolone antibiotics, and other cationic medications) and are instructed in correct timing of lanthanum carbonate administration with respect to drugs that interact with it.

[figure not shown]
C. Study Design and Research Methods

[figure not shown]
Experimental Design. After completing the 12-week Phosphorus Lowering RCT (Figure 1) or 12-week run-in period (Figure 2), a group of 24 research subjects will complete an additional 9-day Phosphorus Balance study. Subjects will provide informed consent for the proposed Balance study. Of note, all research subjects will have an FMD_{BA} measurement at the beginning and end of the parent RCT or the 12-week run-in period. Subjects will continue taking their current dose of active drug (lanthanum carbonate) or placebo from the parent RCT or the 12-week run-in period and will begin a CTRC-prepared fixed low phosphorus diet (daily breakfast, lunch, dinner, and a snack) and will be instructed to consume only deionized water, which will be provided. They will also take polyethylene glycol 1 g with each meal (totaling 3g/day) as a non-absorbable stool marker. After 7 days, subjects will be admitted to the CTRC for a 48-hour admission.

For subjects recruited from the parent Phosphorus Lowering RCT:

- **Session 1:** Recruitment and Consent
 - All subjects currently participating in the parent Phosphorus Lowering RCT will be eligible to participate in the current Phosphorus Balance protocol
- **Session 2:** Beginning of proposed Phosphorus Balance study
 - Blood sampling to monitor serum phosphorus concentration, serum creatinine for measurement of kidney function, and evaluation of markers of mineral metabolism
 - Receive CTRC-prepared fixed low phosphorus diet (daily breakfast, lunch, dinner, and a snack) including deionized water
 - Mifflin St. Joeur equation and activity factor of 1.4 will be used to determine caloric needs. Based on their caloric needs, subjects will be assigned to one of four kilocalorie diet categories: 2000-2300, 2300-2600, 2600-2900, 2900-3200. The subjects will then select their meals from four different pre-set menus.
 - Macronutrients: 15% protein/ 30% fat/ 55% CHO \pm 2% for each macro
 - The diets will contain the same proportion of plant and meat/dairy proteins to control for the different rates of absorption of phosphorus from plant sources versus phosphorus from meat/dairy sources
 - Micronutrients controlled: phosphorus $< 1000 \pm 50$ mg/day and calcium $< 800 \pm 50$ mg/day
 - Each of the 4 kilocalorie group diets will be frozen and sent for exact measurement of phosphorus and calcium content. Subjects will be required to pick-up food in 3-day increments to prevent spoilage
 - Continue current dose of lanthanum or placebo
 - Receive polyethylene glycol 1 g PO TID with meals as a stool marker
 - Submit 1 stool specimen prior to initiating polyethylene glycol to be used as a comparison
- **Session 3:** End of Phosphorus Balance Study
 - 48-hour admission to CTRC
 - Blood sampling to monitor serum phosphorus concentration, serum creatinine for measurement of kidney function, and evaluation of markers of mineral metabolism
 - 24-hour urine and stool collection for phosphorus and calcium measurement (2 will be collected)
 - Subjects will continue 1 g of polyethylene glycol with each meal as a non-absorbable stool marker during the CTRC inpatient admission.
 - Continue CTRC-prepared fixed low phosphorus diet
 - Continue current dose of lanthanum or placebo
 - Final FMD_{BA} measurement to be performed at the UPI Vascular Lab

Figure 1

[figure not shown]
For subjects not enrolled in the parent Phosphorus Lowering RCT:

- **Session 1:** Consent and screening measurements
- **Session 2:** Baseline measurements
 - Resting arterial blood pressure
 - Blood sampling to monitor serum phosphorus concentration, serum creatinine for measurement of kidney function, and evaluation of markers of mineral metabolism
 - FMD_{BA} (endothelium-dependent dilation)
 - Endothelium-independent dilation (EID) to sublingual nitroglycerin
 - Randomization to either lanthanum carbonate or placebo
- **Session 3-5:** Biweekly/monthly check-in (see below)
- **Session 6:** Beginning of proposed Phosphorus Balance study (*same as Session 2 for those recruited from parent Phosphorus Lowering RCT*)
 - Resting arterial blood pressure
 - Blood sampling to monitor serum phosphorus concentration, serum creatinine for measurement of kidney function, and evaluation of markers of mineral metabolism
 - FMD_{BA} (endothelium-dependent dilation) and endothelium-independent dilation (EID) to sublingual nitroglycerin
 - Receive CTRC-prepared fixed low phosphorus diet (daily breakfast, lunch, dinner, and a snack) including deionized water
 - Mifflin St. Jour equation and activity factor of 1.4 will be used to determine caloric needs. Based on their caloric needs, subjects will be assigned to one of four kilocalorie diet categories: 2000-2300, 2300-2600, 2600-2900, 2900-3200. The subjects will then select their meals from four different pre-set menus.
 - Macronutrients: 15% protein/ 30% fat/ 55% CHO \pm 2% for each macro
